3. STUDY DESIGN

3.1. Study Design and Flow Chart

This is an OL proof of concept study of adjunctive GNX treatment in patients with a confirmed clinical diagnosis of TSC and/or a mutation in either the *TSC1* or *TSC2* gene. The trial consists of two parts: Part A consists of a 4-week baseline period followed by a 12-week treatment period (4-week titration and 8-week maintenance). For patients not continuing in the OLE period (Part B), a 2-week taper period followed by a 2-week safety period would follow. The main difference between Part A and Part B is the length of treatment, less frequent assessments, and the ability to alter drug doses (both GNX and other AED treatments which includes initiating and stopping other medications) based on investigator evaluation of the patient's clinical course during Part B. Patients with a seizure frequency reduction rate of $\geq 35\%$ during the 12-week treatment period in Part A compared to baseline may continue into Part B ("OLE eligible"). If the investigator believes there is a medical benefit for the patient who does not meet the seizure reduction criterion to enter the OLE, they must discuss the patient with the sponsor medical monitor and receive sponsor approval for that patient to continue into the OLE.

Part A

- 4-week baseline period

[figure not shown]
IND 044,020
Protocol 1042-TSC-2001Marinus Pharmaceuticals, Inc.
11 Jun 2021

- 4-week titration period
- 8-week maintenance period
- 2-week taper period (For patients who do not complete Part A or after completing Part A but do not continue into Part B)
- 2-week safety follow-up visit post taper (For patients who taper off GNX)

Part B (Optional for OLE-eligible patients)

- OLE period (until the Sponsor markets ganaxolone or terminates the study)
- 2-week taper period (For patients who discontinue GNX due to early termination or completion)
- 2-week safety follow-up visit post-taper (For patients who taper off GNX)

Figure 1: Study Design

GNX = ganaxolone

During the screening visit, each patient's baseline [REDACTED] will be collected and analyzed for post-study evaluation.

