9.6.1. Primary Efficacy Endpoint

The primary efficacy endpoint (change in seizure frequency) is the percent change in 28-day seizure frequency through the end of the 12-week treatment period (4-week titration and 8-week maintenance) relative to the baseline, based on the primary seizure types. The primary seizure types are defined as the following: focal motor seizures without impairment of consciousness or awareness, focal seizures with impairment of consciousness or awareness, focal seizures evolving to bilateral, tonic-clonic convulsive seizures, and generalized motor seizures including tonic-clonic, bilateral tonic, bilateral clonic, or atonic/drop seizures. Focal aware non-motor and generalized seizures without motor features, infantile or epileptic spasms, and myoclonic seizures do not count as the primary seizure types.

Post-baseline 28-day seizure frequency will be calculated as the total number of seizures in the 12-week treatment periods (4-week titration plus 8-week maintenance period) during Part A divided by the number of days with seizure data in the period, multiplied by 28. Baseline 28-day seizure frequency will be calculated as the total number of primary seizures in the baseline period divided by the number of days with seizure data in the baseline period, multiplied by 28.

$$\left(\frac{[(\text{Post-baseline 28-day seizure frequency}) - (\text{Baseline 28-day seizure frequency})]}{(\text{Baseline 28-day seizure frequency})} \right) \times 100\%$$

The baseline, post-baseline, and arithmetic and percent changes from baseline in 28-day seizure frequency will be summarized using descriptive statistics.

The percentages of seizure-free days will be based on the primary seizure types (primary seizure-free-days) and infantile/epileptic spasms (infantile/epileptic spasms free days).

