1.2.1 Primary Efficacy Endpoint

The primary efficacy endpoint (change in seizure frequency) is the percent change in 28-day seizure frequency through the end of the 12-week treatment period (4-week titration and 8-week maintenance) relative to the baseline, based on the primary seizure types. The primary seizure types are defined as the following: focal motor seizures without impairment of consciousness or awareness, focal seizures (motor or non-motor) with impairment of consciousness or awareness, focal seizures evolving to bilateral, tonic-clonic convulsive seizures, and generalized motor seizures including tonic-clonic, bilateral tonic, bilateral clonic, or atonic/drop seizures. Focal aware non-motor and generalized seizures without motor features, infantile or epileptic spasms, and myoclonic seizures do not count as the primary seizure types.

The calculation of post-baseline 28-day seizure frequency and percent change in 28-day seizure frequency are explained in [Section 3.1.3](#).

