1.3 STUDY DESIGN

1.3.1 General Study Design and Plan

This is an open-label (OL) proof of concept study of adjunctive GNX treatment in patients with a confirmed clinical diagnosis of TSC and/or a mutation in either the *TSC1* or *TSC2* gene. The trial consists of two parts ([Figure 1](#)): Part A consists of a 4-week baseline period followed by a 12-week treatment period (4-week titration and 8-week maintenance). For patients not continuing in the 24-week OLE period (Part B), a 2-week taper period followed by a 2-week safety period would follow. The main difference between Part A and Part B is the length of treatment, less frequent assessments, and the ability to alter drug doses (both GNX and other antiepileptic drug [AED] treatments which includes initiating and stopping other medications) based on investigator evaluation of the patient's clinical course during Part B. Patients with a seizure frequency reduction rate of $\geq 35\%$ during the 12-week treatment period in Part A compared to baseline may continue into Part B ("OLE eligible"). If the investigator believes there is a medical benefit for the patient who does not meet the seizure reduction criterion to enter the OLE, they must discuss the patient with the sponsor medical monitor and receive sponsor approval for that patient to continue into the OLE.

The Schedule of Assessments from the protocol for both Part A and Part B are included in Appendix A and Appendix B, respectively, of this document.

Part A

- 4-week baseline period
- 4-week titration period
- 8-week maintenance period
- 2-week taper period (For patients who do not complete Part A or after completing

[figure not shown]
Part A but do not continue into Part B)

- 2-week safety follow-up visit post taper (For patients who taper off GNX)

Part B (Optional for OLE-eligible patients)

- 24-week OLE period
- 2-week taper period (For patients who discontinue GNX due to early termination or completion)
- 2-week safety follow-up visit post-taper (For patients who taper off GNX)

Figure 1: Study Design

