3.1.3.2 Post-baseline seizure frequency – Maintenance Period, Part A, Part B and Overall

Post-baseline 28-day seizure frequency will be calculated as the total number of seizures in the specified post-baseline period divided by the number of days with non-missing seizure data in the same post-baseline period, multiplied by 28. Within Part A of the study, post-baseline seizure activity will be determined based on the days following the first day after the date of the first dose of IP. The first day of treatment is included in neither the baseline nor the post-baseline period since seizures reported on that date could have occurred either before or after the initiation of treatment. Within Part B (OLE

period), post-baseline seizure activity will be determined by the first day of OLE treatment.

Separate frequencies will be calculated for the 8-week maintenance period of Part A (Maintenance), Parts A (12-week treatment period consisting of a 4-week titration period and an 8-week maintenance period) and B of the study (OLE period of up to 24 weeks) and across both study parts.

Post-baseline specified study period 28-day seizure frequency =

$$\frac{\# \text{ seizures, specified study period}}{\# \text{ specified study period days with seizure data reported}} \times 28$$

3.1.3.3 Percent change in 28-day seizure frequency – Maintenance Period, Part A, Part B and Overall

% change from baseline =

$$\frac{[(\text{post-baseline 28-day seizure frequency}) - (\text{baseline 28-day seizure frequency})]}{(\text{baseline 28-day seizure frequency})} \times 100$$

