3.2 ANALYSIS VISIT WINDOWS

Efficacy Analyses

Efficacy analyses will use data only from scheduled visits. Data will be reported by designated visit.

Data collected at unscheduled visits will be provided in listings.

For analysis of data collected across specific study periods, the following definitions will be applied:

- Baseline period: Visit 1 to Visit 2; Study Week -4 (Day -32 ± 4) through Study Day 0 (date of first dose of IP)
- Titration period: Visit 2 + 1 day to Visit 4; Study Day 1 through Study Week 4 (Day 28 ± 3 days; date of Visit 4)
- Maintenance period: Visits 4 + 1 day and 5; Study Week 5 (± 3 days) through Study Week 12 (± 3 days)
- 12-week treatment period: titration period + maintenance period (including taper and safety visits if not continuing in OLE)
- OLE period if continuing in OLE: Visit 5 + 1 day through final visit

Safety Analyses

Safety data will be summarized by actual visit. No visit windowing will be applied.

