4.2 EFFICACY ANALYSES

4.2.1 Primary Efficacy Analysis

4.2.1.1 Primary Analysis

The primary efficacy endpoints, the percent change in 28-day primary seizure type frequency through the end of the 12-week treatment period (Part A; 4-week titration and 8-week maintenance) relative to the baseline, is defined in Section 1.2.1. The calculation of the primary endpoint is described in Section 3.1.3.

Descriptive summaries including the number of patients with non-missing primary seizure data, mean arithmetic change and percent change in 28-day primary seizure type frequency from baseline and associated 95% confidence intervals, SD, minimum, median and maximum values will be presented for the baseline period, 4-week titration period, 8-week maintenance period and 12-week treatment period. All patients in the ITT population and all available seizure data within Part A of the study will be included in these analyses regardless of whether the patient stopped taking IP or took rescue medication.

Additionally, a by-patient listing of seizure data collected during Part A will be provided.

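### SAP 3.2 stretches the 12-week primary window to about 16 weeks, but only for patients who do not enter the extension

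*SAP*

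**What the plan says.** Four places give the window as 4 + 8 weeks:

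- Protocol 9.6.1 counts the "total number of seizures in the 12-week treatment periods (4-week titration plus 8-week maintenance period) during Part A".
- SAP 1.2.1 defines the endpoint as the "percent change in 28-day seizure frequency through the end of the 12-week treatment period (4-week titration and 8-week maintenance" weeks.
- SAP 3.1.3.2, the derivation, refers to "Parts A (12-week treatment period consisting of a 4-week titration period and an 8-week maintenance period".
- SAP 4.2.1.1 describes the endpoint as running "through the end of the 12-week treatment period (Part A; 4-week titration and 8-week maintenance) relative to the baseline".

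SAP 3.2, under its Efficacy Analyses heading, sets the period definitions to be applied to data collected across study periods. There the period becomes "12-week treatment period: titration period + maintenance period (including taper and safety visits if not continuing in OLE".

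SAP 4.2.1.1 goes on to say that "all available seizure data within Part A of the study will be included in these analyses". Both documents list taper and safety follow-up under Part A: Protocol 3.1 has a "2-week taper period (For patients who do not complete Part A or after completing Part A but do not continue into Part B", and SAP 1.3.1 has the same bullet.

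**The concern.** The SAP contradicts itself on the window of its primary endpoint. SAP 3.1.3.2 gives the formula but no end date for Part A. The visit and day limits that a programmer would use for the end of that period are in 3.2, which is the section with the extra wording.

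The added time is not neutral. It applies only to patients who do not continue, and it consists of days on a falling dose or off drug. Continuation is decided at Visit 5, mainly on a reduction of at least 35% in primary seizures over the Part A treatment period (Protocol 4.1.1). Part B is optional and sponsor-approved exceptions exist (Protocol 3.1), so the link is partial. Still, the result over the first 12 weeks helps decide whether four more weeks are averaged into that same result. The 50% responder endpoint (SAP 1.2.2.1) uses the same period and inherits the problem.

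**Working it through.** **Window length.** Titration 4 + maintenance 8 = 12 weeks = 84 days, which reproduces the stated period. Adding 2 weeks of taper and 2 of follow-up gives 16 weeks = 112 days, matching Visit 5a at Week 16 (Protocol 7.2.8). The extra 28 days are 28/112 = 25% of the longer window. Visits 5 and 5a each have a ±3-day window. The extra time is 25 to 31 days if Visit 5a is timed from the end of treatment, or 109 - 87 = 22 to 115 - 81 = 34 days if the two visits vary independently.

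**Effect on one non-continuing completer.** Set the baseline rate to 1 and the 12-week rate ratio to r, with complete diaries. The documents give no rates after Week 12, so four courses are assumed:

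| Course after Week 12 (assumed) | 16-week ratio | r = 0.8 (-20%) | r = 0.7 (-30%) | r = 1.1 (+10%) | 12-week reduction needed to count as a 50% responder |
|---|---|---|---|---|---|
| Effect persists | r | -20.0% | -30.0% | +10.0% | 50.0% |
| Half effect in taper, then baseline | (13r + 3)/16 | -16.3% | -24.4% | +8.1% | 61.5% (r ≤ 5/13) |
| Baseline throughout | (12r + 4)/16 | -15.0% | -22.5% | +7.5% | 66.7% (r ≤ 1/3) |
| Baseline in taper, then 25% above | (12r + 4.5)/16 | -11.9% | -19.4% | +10.6% | 70.8% (r ≤ 3.5/12) |

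**Responder count.** The main way to change it is to lose a patient who reduced by 50% or more and did not continue. A patient below the 35% criterion (r > 0.65) could become a responder only if (12r + 4x)/16 ≤ 0.5, where x is the rate after Week 12 relative to baseline. That requires x < (8 - 7.8)/4 = 0.05.

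**Group mean.** The shift is linear in r, so it equals the fraction not continuing times the shift at their mean r. Assume 10 to 20 of 30 do not continue, with a mean 12-week change between -20% and +10%:

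- Most favourable to the drug: (20/30)(1.075 - 1.10) = -1.7 points.
- Least favourable over the four courses: (20/30)(0.88125 - 0.80) = +5.4 points.
- If the rate ran 25% above baseline for all 28 days: (20/30)(0.9125 - 0.80) = +7.5 points.

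This range illustrates the size and is not a bound. It leaves out early stoppers and says nothing about the median.

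**Early stoppers.** If Visit 5a follows the patient's own taper and s is the last full-dose day, the extra days are max(0, s + 28 - 84), that is 0 to 28. If Visit 5a stays at Week 16, there are 28.

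**A separate minor point in SAP 3.2.** The end of titration is labelled both as Day 28 ± 3 (Day 25 to 31) and as the date of Visit 4. Visit 4 is Week 5 ± 3 days (Protocol 7.2.6), or Day 32 to 38, so the two ranges cannot overlap. A split at Visit 4 makes the 8-week maintenance period nominally 84 - 35 = 49 days (81 - 38 = 43 to 87 - 32 = 55) instead of 56. This touches only the titration and maintenance summaries.

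**The case against.** The best reply is that the intended window is plain. The endpoint definition, the derivation, the analysis section and the protocol all say 4 + 8, and one parenthesis in a visit-window section should not outweigh them. Part A is also often used in the narrow sense: Protocol 3.1 calls it a 16-week period (4 baseline + 12 treatment) and says that taper follows. The parenthesis might have been meant only for early stoppers whose taper falls inside the 12 weeks, or only as a visit label.

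The first part is fair as a guess at intent, but the text does not settle it. Usage of Part A is mixed, since the same Protocol 3.1 and SAP 1.3.1 list taper and safety follow-up under it. The condition in 3.2 covers every patient not continuing, including those who finish Week 12 and then taper. Nor is it only a visit label. Visit 5a is a scheduled visit, and the diary is the only efficacy information reviewed there, so in an efficacy section the wording can act only on seizure counts.

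Two further points stand. The study has no hypothesis test or decision threshold, which limits the harm. The sizes above also depend on assumed rates and an assumed number of non-continuers. The contradiction is certain, but its numerical consequence is not.

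**Conclusion.** The concern holds. As written, SAP 3.2 gives non-continuing completers a primary window a third longer than that of extension entrants (28/84), and the split is driven largely by the outcome. Which section is programmed would change the reported percent change for those patients. Under the assumed courses, -20% becomes something between -20.0% and -11.9%. The trial-level mean would probably move by a few points, with uncertain size and direction. The responder count could fall if any patient with a reduction of 50% or more does not continue, or if early stoppers have diary data after Week 12. A gain from patients below the 35% criterion is possible only if seizures almost cease after Week 12.

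The estimates and their 95% intervals are the whole efficacy result here, so the window should be unambiguous. This should be corrected, but it does not undermine the trial.

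**What to change.** 1. In SAP 3.2, delete the parenthesis on taper and safety visits and end the 12-week window at Visit 5 for every patient. If Visit 5 is missing, end it on the date of first dose + 84 days. A calendar rule is safer than a day number, because that date is Day 84 under SAP 3.2 (first dose is Day 0) and Day 85 under the SAP 3.1.2 formula (first dose is Day 1). Reconcile those two sections. Keep off-drug diary days that fall inside the window, as SAP 4.2.1.1 already intends.
2. In SAP 4.2.1.1, refer to seizure data within the 12-week treatment period, not within Part A.
3. List non-continuers' seizures separately from the day after the cut-off, so that taper days inside the window are not counted twice.
4. Minor: split the titration and maintenance summaries at the end of Week 4 on the same date convention, not at Visit 4.

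Items 1 and 2 resolve the contradiction; 3 and 4 are tidying. The cost is SAP wording and one programming window, with no new data.

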3.3 PREMATURE WITHDRAWAL AND MISSING DATA

Available data from patients who withdraw from the study prematurely will be included in analyses, unless otherwise indicated. Only observed data will be summarized. No data

will be imputed or carried forward for missing values or for patients who discontinue early.

All missing data and missing or partial dates for AEs and medications will be queried for a value. In the unlikely event that no value can be obtained, substitutions will be made as described below.

3.3.1 Missing and Partial Start/Stop Dates - AEs and Concomitant Medications

The handling of partial start and stop dates for AEs are described in Table 3 below. Similar algorithms for handling missing and partial dates of concomitant medication usage are described in Table 4. In both cases, if a stop date is complete and an imputed start date is after the stop date, the start date will be set to the stop date.

Table 3: Adverse Event Start/Stop Date Imputation

Parameter	Missing	Additional Conditions	Imputation
Start date for AEs	D	M and Y same as M and Y of first dose of IP	Date of first dose of IP
		Y same but M prior to month of first dose of IP	Last day of month
		Y same but M after month of first dose of IP	First day of month
		Y is prior to year of first dose of IP	Last day of month
		Y is after year of first dose of IP	First day of month
	M	Y is same as Y of first dose of IP	Month of first dose of IP
		Y is prior to year of first dose of IP	M = December
		Y is after Y of first dose of IP	M = January
	D and M	Y same as Y of first dose of IP	Date of first dose of treatment
		Y prior to Y of first dose of IP	M and D will be December 31
		Y after Y of first dose of IP	M and D will be January 1
	Y, or M, D, Y	Y and/or start date missing	Date of first dose of treatment
Stop date for AEs	D	M and Y not missing	Use last day of month (i.e. D may take on values of 28, 29, 30, or 31, depending on month)
	M	Y not missing; if D also missing, impute D as described above	M = December
	Y, or M, D, Y	Y and/or stop date missing.	No imputation. Date left missing.

D=day, M=month, Y=year

Note: In all cases, if an estimated start date is after a complete stop date, the start date will be set to the AE stop date.

Similarly, if the estimated stop date is before a complete or imputed start date, use the last day of the start date month.

Table 4: Imputation for Prior/Concomitant Medication Missing and Partial Dates

Parameter	Missing	Additional Conditions	Imputation
Start date for con meds	D only	M and Y are not missing or imputed.	Use 1 st day of M.
	M only	D and Y are not missing or imputed.	M = January
	M and D	Y is not missing or imputed.	Use Jan 01 of Y
	M, D, and Y	None - date completely missing	No imputation but considered concomitant unless stop date is prior to first dose of IP.
Stop date for con meds	D only	M and Y are not missing or imputed.	Last day of month
	M only	D and Y are not missing or imputed.	M = December
	M and D	Y is not missing or imputed	Use Dec 31 of Y
	M, D, and Y	None - date completely missing and NOT ongoing	No imputation

Note: In all cases, if an estimated start date is after a complete stop date, the start date will be set to the end date of medication.

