4.3.2 Adverse Events

Adverse events (AEs) are collected from the time of informed consent/assent through the defined follow-up period. AEs are coded using MedDRA dictionary, version 22.0 and are categorized by system organ class (SOC) and preferred term (PT). A treatment-emergent AE (TEAE) is defined as an AE that starts or worsens on or after the first day of dosing with IP. Analyses of TEAEs for Part A of the study will include AEs that start or worsen during Part A and will not include any AE that starts or worsens during Part B. For Part B of the study, TEAEs will be include events that start or worsen after the first day of Part B relative to the first day of Part B. TEAEs over the entire study will be summarized for patients who participate in both Parts A and B of the study.

Tabulations of AEs will be by patient such that an individual is only counted once per summary category. Detailed by-patient listings of all AEs reported during the study will be provided and will include verbatim and coded terms for each AE.

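### SAP Table 3 sets no floor at the first dose when only the month of an AE start is missing, so a post-dose event can drop out of the TEAE tables; secondarily, no row uses the Part B start

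*SAP*

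**What the plan says.** SAP 3.3.1, Table 3, imputes AE start dates as follows.

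- **Month missing, first-dose year:** the month becomes the "month of first dose of IP". The recorded day is kept.
- **Month missing, later year:** the month becomes January.
- **Day missing:** the first-dose date if the AE falls in the first-dose month. For a later month the rule is "First day of month".
- **Day and month missing:** "Date of first dose of treatment" if the year is the first-dose year; "M and D will be January 1" if the year is later.
- **Year or whole date missing:** the first-dose date.

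The only consistency check on an imputed start is that "if an estimated start date is after a complete stop date, the start date will be set to the AE stop date". It moves a date backwards, never forwards.

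SAP 4.3.2 then classifies events by date: "A treatment-emergent AE (TEAE) is defined as an AE that starts or worsens on or after the first day of dosing with IP". On study part it says "Analyses of TEAEs for Part A of the study will include AEs that start or worsen during Part A" and that these analyses "will not include any AE that starts or worsens during Part B". Part B TEAEs are those starting or worsening after the first day of Part B. SAP 3.3 says that missing and partial dates are queried first and substituted only if no value can be obtained.

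**The concern.** An imputation rule for AE start dates should not remove an event that may be treatment-emergent. The ambiguous rows of Table 3 follow that principle by falling back on the first-dose date. The month-only row does not. An event with a known day can be dated before dosing, whereas the same event with neither day nor month known would count as a TEAE. More information therefore gives a less cautious result.

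The secondary issue is that SAP 4.3.2 splits TEAEs between Part A and Part B by date, while Table 3 knows only one anchor, the first dose of the study. Long-term safety in Part B is a secondary objective (protocol 2.2.2; SAP 1.1.2), so an event that moves to Part A leaves the table meant to address that objective.

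**Working it through.** The plan gives no figure to reproduce. The check applies the Table 3 rules first to single dates and then to all date combinations.

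**Step 1: when the month-only row fails.** The imputed start is (recorded year, month of first dose, recorded day). It falls before the first dose exactly when the onset year is the first-dose year and the recorded day is smaller than the day of the first dose. The stop-date check does not help: a stop on 20 August 2020 is later than an imputed 5 June 2020, so nothing changes.

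**Step 2: worked dates.** SAP 3.2 starts the OLE period one day after Visit 5 (Week 12). Here Part B is taken to start at first dose + 84 days.

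| First dose / Part B start | Missing | True onset (part) | Imputed | Counted in |
|---|---|---|---|---|
| 20 Jun 2020 / 12 Sep 2020 | month | 5 Aug 2020 (A) | 5 Jun 2020 | pre-dose, not a TEAE |
| same | month | 5 Oct 2020 (B) | 5 Jun 2020 | pre-dose, not a TEAE |
| same | month | 25 Oct 2020 (B) | 25 Jun 2020 | Part A |
| same | day and month | 10 Nov 2020 (B) | 20 Jun 2020 | Part A |
| same | day | 20 Sep 2020 (B) | 1 Sep 2020 | Part A |
| same | day | 20 Oct 2020 (B) | 1 Oct 2020 | Part B |
| same | day and month | 1 Feb 2021 (B) | 1 Jan 2021 | Part B |
| 10 Dec 2020 / 4 Mar 2021 | day and month | 3 May 2021 (B) | 1 Jan 2021 | Part A |

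**Step 3: shares, given that a date is incomplete in the stated way.** Share = (pairs of first-dose date and true onset day that land in the category) / (all pairs). Onset runs over days 0–83 for Part A and days 84–251 for Part B (168 days, the SAP's 24 weeks). Two assumptions are not in the documents: onset is uniform within each part, and first doses are spread evenly over the window shown.

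| First-dose window | Month missing: true A to pre-dose | Month missing: true B to pre-dose | Month missing: true B to A | Day and month missing: true B to A | Day missing: true B to A |
|---|---|---|---|---|---|
| Apr 2020–May 2021 | 39.1% | 27.3% | 47.4% | 79.2% | 8.8% |
| Calendar 2021 | 38.1% | 24.6% | 47.1% | 76.8% | 8.8% |
| Apr–Sep 2020 | 44.9% | 25.8% | 32.2% | 58.6% | 8.9% |
| Oct 2020–Mar 2021 | 31.3% | 23.3% | 62.1% | 95.2% | 8.7% |

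A wholly missing date sends 100% of true Part B events to Part A. In the day-missing, day-and-month-missing and wholly-missing rows, no true Part A or Part B event becomes pre-dose. About 1% of month-only cases give an impossible date, such as 31 June.

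**Step 4: longer Part B.** SAP 1.3.1 gives Part B 24 weeks. Protocol 3.1 keeps the OLE open until marketing or termination. With Part B onsets spread over 48 weeks and the calendar-2021 window, the day-and-month share falls from 77% to about 54% and the day-only share from 9% to about 4%.

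**Step 5: scale.** With about 30 treated patients, one patient is 1/30 = 3.3 percentage points in a Part A table. The count changes only if the patient has no other event in that category.

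**The case against.** The case for leaving the rule alone has several parts, and much of it stands.

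- Dates are queried first, and a known day with an unknown month is an unusual pattern. This stands: few events will reach the rule.
- All AEs are listed by patient, and the SAE summary (SAP 4.3.2.5) is not restricted to TEAEs. An SAE is therefore not lost. This stands.
- Protocol 8.1 treats every AE reported after the start of IP as treatment-emergent. This helps only in part. SAP 4.3.2 uses the start date, so the two definitions can disagree for exactly these events.
- AEs are collected from consent, so a pre-dose date is sometimes correct. This is true for screening-period events, and the fix must leave alone those whose known date parts or stop date show it.
- Anchoring unknown dates to the first dose is a defensible convention, and an event moved from Part B to Part A stays in the whole-study TEAE summary. This stands, and it is why the Part B point is secondary.

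A reader might infer that about half of month-only-missing events are lost, because two independent uniform days in a 30-day month give 435/900 = 48%. The documents do not support that as a share of all such events. The row applies only in the first-dose year, a later year goes to January, and onset day and dosing day are not independent soon after dosing. The figure lies above every range in the check.

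**Conclusion.** The month-only row is wrong as written: it can date a post-dose AE before the first dose, against the convention of the neighbouring rows. Given such a date, and assuming uniform onset within each part and a 24-week Part B, about 31–45% of true Part A events and 23–27% of true Part B events lose TEAE status. The documents give no rate of partial dates, so the number of events cannot be computed. It is probably very small. The study is descriptive, and no efficacy estimate or decision rule uses these dates, so severity is minor.

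The secondary point also holds within limits. Some partly dated Part B events are tabulated in Part A: about 59–95% with day and month missing, depending on the first-dose window and lower if Part B is longer; about 9% with only the day missing; and all with no date. A reader might infer that partly dated Part B events generally move to Part A. They do not: about 91% of those missing only the day stay in Part B.

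Nor does this point extend to the medication dates in Table 4. That table has no first-dose-month row, and medications have no TEAE status to lose.

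**What to change.** 1. Add one line to Table 3: if the imputed start is before the first dose, and neither the known date parts nor a complete stop date exclude an on-treatment start, set it to the first-dose date. In the worked case, 5 June 2020 becomes 20 June 2020 and the event is a TEAE. With a first dose on 20 December and a recorded day of 5 in the same year, every possible date is before dosing, so the imputed date stands.
2. For the split by part, list the AEs whose incomplete start date is compatible with either part, and state how they are assigned. A rule based on when an event was first recorded is not advised. The SAP defines no such variable, and the rule would push late-reported Part A events into Part B.

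The cost is one line in Table 3, one sentence on assignment, one short listing and the matching programming specification. Trial conduct does not change. Some true screening-period events with a missing month may be counted as TEAEs, the same cautious direction as the other ambiguous rows.
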